1. INTRODUCTION

The bacterium *Streptococcus pneumoniae* kills half a million children before their fifth birthday annually, mostly in low-resource areas of the world. The most common cause of childhood morbidity and mortality due to the bacterium is pneumonia, which in 2013 was estimated to be the cause of roughly 900,000 under-five deaths worldwide, making it the deadliest infectious disease of young children today.

The Serum Institute of India (SIIPL), in collaboration with the PATH Center for Vaccine Innovation and Access (CVIA), has been working since 2006 to develop a multivalent pneumococcal conjugate vaccine (PCV) designed to be affordable for use in low resource countries. PNEUMOSIL, SIIPL's 10-valent candidate PCV, incorporates those pneumococcal serotypes most prevalent prior to PCV introduction in cases of invasive pneumococcal disease (IPD) in Africa, Asia, and Latin America (types 1, 5, 6A, 6B, 7F, 9V, 14, 19A, 19F, and 23F), thus offering comparable coverage to currently licensed PCVs in these settings.

Previous clinical studies have provided the necessary immunogenicity, safety, and tolerability data to support the World Health Organisation (WHO) prequalification of PNEUMOSIL when delivered in a 3-dose primary schedule (3+0). The current study (CVIA 074) is intended to provide additional data to assist the WHO Prequalification Programme and regulatory authorities in making recommendations regarding the immunogenicity and safety of PNEUMOSIL when delivered in a 2-dose primary and booster (2+1) schedule, and to compare immunogenicity to that of currently licensed second-generation PCVs (Prevenar 13 and Synflorix) when administered in the same 2+1 schedule.

Version 4.0 of the statistical analysis plan (SAP) is an expanded version of the summary plan included in Protocol CVIA 074 (version 3.0). Cumulative changes made to the SAP since approval of protocol Version 1.0 are documented in the Appendix. Mock tables, listings, and figures (TLFs) designed to capture results of analyses will be approved by the Study Clinical Lead prior to un-blinding and maintained in a separate document.

2. STUDY OBJECTIVES AND ENDPOINTS

2.1. Study Objectives

2.1.1. Primary Objectives

Immunogenicity:

1. To evaluate the serum IgG antibody responses (geometric mean concentrations [GMCS]) to the 10 serotypes in PNEUMOSIL, alone and in comparison to IgG antibody responses to these serotypes induced by Prevenar 13 and Synflorix, at 4 weeks post booster dose (administered at 9-18 months of age)

Safety and Tolerability:

1. To assess the safety and tolerability of a 2-dose primary series and booster dose of PNEUMOSIL co-administered with routine pediatric vaccines, through 4 weeks post booster dose.

2.1.2. Secondary Objectives:**Immunogenicity:**

1. To evaluate the functional serum antibody responses (geometric mean titers [GMTs]) to the 10 serotypes in PNEUMOSIL as measured by Opsonophagocytic Assay (OPA), alone and in comparison to the responses to these serotypes induced by Prevenar 13 and Synflorix, at 4 weeks post booster dose (subset of 50 subjects per group)
2. To assess seroresponse rates (IgG antibody levels and functional responses) to the 10 serotypes in PNEUMOSIL, alone and in comparison to seroresponse rates for these serotypes induced by Prevenar 13 and Synflorix, at 4 weeks post booster dose (subset of 50 subjects per group for functional response rates)
3. To evaluate the serum IgG antibody responses (seroresponse rates and GMCs) to the 10 serotypes in PNEUMOSIL, alone and in comparison to antibody responses to these serotypes induced by Prevenar 13 and Synflorix, at 4 weeks post completion of primary vaccination (administered at 6 and 14 weeks of age)
4. To evaluate the functional serum antibody responses (seroresponse rates and GMTs) to the 10 serotypes in PNEUMOSIL as measured by OPA, alone and in comparison to the functional antibody responses to these serotypes induced by Prevenar 13 and Synflorix, at 4 weeks post completion of primary vaccination (subset of 50 subjects per group)
5. To evaluate the persistence of the post-primary serum IgG antibody responses (seroresponse rates and GMCs) to the 10 serotypes in PNEUMOSIL, alone and in comparison to IgG antibody responses to these serotypes induced by Prevenar 13 and Synflorix, at 9-18 months of age (prior to a booster dose)
6. To evaluate the persistence of post-primary functional serum antibody responses (seroresponse rates and GMTs) to the 10 serotypes in PNEUMOSIL as measured by OPA, alone and in comparison to the functional antibody responses to these serotypes induced by Prevenar 13 and Synflorix, at 9-18 months of age (subset of 50 subjects per group prior to booster)
7. To evaluate the booster responses [(serum antibody concentrations (GMC) and functional responses (GMT)] to PNEUMOSIL, alone and in comparison to booster responses to Prevenar 13 and Synflorix, from 4 weeks after completion of primary vaccination to 4 weeks after a booster dose (subset of 50 subjects per group for functional responses)

2.2. Study Endpoints

2.2.1. Primary Endpoints:

Immunogenicity:

1. Serotype-specific serum IgG GMCs measured 4 weeks post booster dose

Safety and Tolerability:

1. Number and severity of solicited local and systemic adverse events (AEs) through Day 6 post each vaccination
2. Number, severity and relatedness of all unsolicited AEs until 9 months of age, and from booster vaccination through a 4-week follow-up period
3. Number, severity, and relatedness of all serious adverse events (SAEs) through the entire study period

2.2.2. Secondary Endpoints:

Immunogenicity:

For Secondary Objective 1 (post-booster OPA GMTs):

- Serotype-specific serum OPA GMTs measured 4 weeks post booster dose

For Secondary Objective 2 (post-booster seroresponse rates):

- Percentage of subjects with serotype-specific serum IgG concentrations $\geq 0.35 \mu\text{g/mL}$ measured 4 weeks post booster dose
- Percentage of subjects with serotype-specific serum IgG concentrations $\geq 1.0 \mu\text{g/mL}$ measured 4 weeks post booster dose
- Percentage of subjects with serotype-specific serum OPA titers ≥ 8 measured 4 weeks post booster dose

For Secondary Objective 3 (post-primary IgG responses):

- Percentage of subjects with serotype-specific serum IgG concentrations $\geq 0.35 \mu\text{g/mL}$ measured 4 weeks post completion of primary vaccination
- Serotype-specific serum IgG GMCs measured 4 weeks post completion of primary vaccination

For Secondary Objective 4 (post-primary OPA responses):

- Percentage of subjects with serotype-specific serum OPA titers ≥ 8 measured 4 weeks post completion of primary vaccination
- Serotype-specific serum OPA GMTs measured 4 weeks post completion of primary vaccination

For Secondary Objective 5 (persistence of post-primary IgG responses):

- Percentage of subjects with serotype-specific serum IgG concentrations $\geq 0.35 \mu\text{g/mL}$ measured prior to booster dose
- Serotype-specific serum IgG GMCs measured prior to booster dose

For Secondary Objective 6 (persistence of post-primary OPA responses):

- Percentage of subjects with serotype-specific serum OPA titers ≥ 8 measured prior to booster dose
- Serotype-specific serum OPA GMTs measured prior to booster dose

For Secondary Objective 7 (booster effects):

- Ratio of serotype-specific serum IgG GMCs measured 4 weeks post booster dose to serotype specific IgG GMCs measured 4 weeks post completion of primary vaccination
- Ratio of serotype-specific serum OPA GMTs measured 4 weeks post booster dose to serotype specific serum OPA GMTs measured 4 weeks post completion of primary vaccination

3. STUDY DESIGN

This is a prospective, single center, randomized, active-controlled, observer-blind, Phase 3 descriptive study in which 660 healthy Gambian PCV-naïve infants will be randomized 1:1:1 to receive 3 doses of PNEUMOSIL, Synflorix, or Prevenar 13.

3.1. Visit Schedule and Evaluations

Study vaccinations will be scheduled to occur at 6 weeks of age (+2 week visit window; Visit 1 [V1]), 14 (+2) weeks of age (V3), and 9-18 (+1) months of age (V5). Standard Expanded Program on Immunization (EPI) vaccinations in The Gambia (except Prevenar 13) will be given concomitantly with each primary dose of study vaccine, at 10 (+2) weeks of age (V2), and at 9 months of age where reasonable (recognizing the impact of SARS-CoV-2 on the feasibility of clinic visits). Blood draws for immunogenicity assessments will occur 4 (+2) weeks after the second study vaccination (V4), immediately prior to booster vaccination (V5) at 9-18 months of age, and at 4 (+2) weeks after booster vaccination (V6), which serves as the end-of-study visit. All subjects with evaluable specimens will be assessed for serum IgG responses. For functional antibody responses, 50 subjects who completed V4 per protocol and intended to continue to V6

were selected from each treatment group for OPA specimen testing. Subjects who did not complete V5 or V6 per protocol were replaced with new subjects from the same field site and treatment group to contribute V5 and V6 OPA data (see Section 3.5). The study schema is presented in Table 1.

Table 1. Study Schema

Visit / Age (with length of visit window in parentheses)					
V1	V2	V3	V4	V5	V6
6 (+2) wks	10 (+2) wks	14 (+2) wks	V3+4 (+2) wks	9-18 (+1) mo	V5+4 (+2) wks
X, E	E	X, E	B	B, X, E	B

wks = weeks, mo = months, X = study vaccination, E= EPI vaccines, B = blood sample for immunogenicity testing

Solicited reactogenicity events (REs) and vital signs will be assessed at 30 (+/- 10) minutes following each study vaccination. Solicited local REs include tenderness, erythema/redness, and induration/swelling at the injection site. Solicited systemic REs include cutaneous rash, fever, irritability, drowsiness, and decreased appetite. In addition to in-clinic assessments on the day of vaccination, all subjects will be monitored by field workers for local and systemic reactogenicity events during the 6 days after each study vaccination administration.

3.2. Sample Size and Power Calculations

Sample size considerations are based on expected precision of immunogenicity-related parameter estimates, rates of Treatment Emergent Adverse Events (TEAEs), and descriptive comparisons between treatment groups in these measures. All sample size calculations assume the use of descriptive 95% confidence intervals (CIs), with no adjustment for multiple comparisons. Unless otherwise noted, asymptotic Wald-type CIs will be used when describing proportions, and likelihood Score-type intervals for differences in proportions. Log-normality will be assumed when computing CIs for GMCs, GMTs, and their ratios. All sample size calculations were performed using SAS (v9.4).

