12.1. Sample Size Considerations

Previous clinical studies have provided the necessary immunogenicity, safety, and tolerability data to support WHO pre-qualification (PQ) of PNEUMOSIL. The current study is intended to provide additional data to assist WHO-PQ and regulatory authorities in making recommendations regarding the immunogenicity and safety of PNEUMOSIL when delivered in a 2+1 dosing schedule. Since there are no hypothesis tests specified in this supportive study, sample size considerations are based on expected

precision of immunogenicity-related parameter estimates, rates of AEs, and descriptive comparisons between treatment groups in these measures, which are considered sufficient by the study team to generate actionable data by regulatory authorities.

All sample size calculations assume the use of descriptive 95% CIs (both for treatment group-specific measures and differences between groups), with no adjustment for multiple comparisons. Unless otherwise noted, asymptotic Wald-type CIs will be used when describing proportions, and asymptotic likelihood Score-type intervals for differences in proportions. Log-normality will be assumed when computing CIs for GMCs, GMTs, and their ratios between groups.

Primary Immunogenicity Objective:

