3.2.2. Primary Safety Objective

With a sample size of 220 per group, there is 89% or greater chance of observing at least 1 safety endpoint (e.g., a solicited RE) which occurs with probability 0.01 or more. If no events of a specific classification occur, then the 95% upper confidence bound for the event rate will be at most 0.017.

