3.5. Selection of OPA Specimens

Prior to the interim analysis of primary series immunogenicity data, the PI provided the ratio of subject enrolments per field site expected to be achieved at the completion of the trial. Based on this ratio, the independent statistician selected (based on order of entry into the study, not randomly) the first 27 subjects with evaluable V4 specimens in each treatment group from the Brikama field site, and the first 23 subjects with evaluable V4 specimens in each treatment group from the Bundung site, such that a total of 50 subjects per group were selected for OPA analysis proportional to the enrolment total in each site. Selected subjects who did not complete V5 per protocol were later replaced with new subjects from the same field site and treatment group to contribute V5 and V6 OPA data (with replacements also selected in order of enrolment date, not randomly). If more than 10% of subjects fail to contribute evaluable results at a given visit, then additional subjects may have their specimens analysed to help ensure at least 45/group contribute to each secondary functional antibody analysis timepoint. The PATH Clinical Lead will make this determination in blind review of data once the availability of OPA results has been determined for all selected subjects.

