5. EVALUATION OF IMMUNOGENICITY

Analysis Populations: Primary and secondary immunogenicity will be evaluated within the Primary and Secondary Per Protocol Immunogenicity Populations, as noted in Table 3.

Data Sources: Primary immunogenicity objectives will be based on serotype-specific IgG antibody concentrations measured 4 weeks after the booster vaccination series (V6). Secondary objectives will be based on the serotype-specific IgG concentrations and OPA titers at three time points (4-weeks after completion of the primary series (V4), immediately prior to booster (V5), and V6).

Endpoint Definitions:

1. **GMC [or GMT]:** The geometric mean concentration (or titer) = antilog (mean $[\log_{10} x]$), where x is the assay result
2. **Response to study vaccine:**
 - IgG concentration $\geq 0.35 \mu\text{g/mL}$
 - IgG concentration $\geq 1.00 \mu\text{g/mL}$
 - OPA titer ≥ 8

5.1. General Comments on Reporting of Immunogenicity Objectives:

1. Differences in proportions of responders to each serotype in PNEUMOSIL will be reported as the PNEUMOSIL proportion minus the reference group (Synflorix or Prevenar 13) proportion, with 95% confidence intervals calculated using the Miettinen-Nurminen (1985) likelihood score method. If the response rate is 100% in each group, then two non-response records (one for each group) will be included and given a weight of 0.000001 to facilitate computation of the 95% CI. Differences in proportions will be considered statistically significant if the 95% CI excludes 0.
2. Within-group GMCs [GMTs] and 95% CIs for each serotype in PNEUMOSIL will be computed based on the antilog (base 10) of mean log10 concentrations [titers] and the corresponding CI limits for the mean log10 values, based on a log-normality assumption.
3. Between-group GMC [GMT] ratios will be reported as the PNEUMOSIL GMC [GMT] divided by the reference vaccine GMC [GMT]. 95% CIs for between-group GMC [GMT] ratios will be computed based on the antilog (base 10) of the corresponding CI limits for the difference in mean log10 concentrations [titers]. Differences between groups will be considered statistically significant if the 95% CI excludes 1.

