5.3.2. Secondary Objective 2: IgG seroresponse rates 4 weeks post booster

Secondary objective 2 is to assess seroresponse rates (IgG antibody levels and functional responses) to the 10 serotypes in PNEUMOSIL, alone and in comparison to seroresponse rates for these serotypes induced by Prevenar 13 and Synflorix, at 4 weeks post booster dose (functional responses assessed in a subset of 50 subjects per group). For each serotype, the proportion of responders (IgG concentrations $\geq 0.35 \mu\text{g/mL}$; IgG concentrations $\geq 1.0 \mu\text{g/mL}$; and OPA titers ≥ 8) at 4 weeks post booster will be reported, together with 95% CIs for the proportions and for differences between the PNEUMOSIL and comparison groups. Differences between groups will be considered statistically significant if the 95% CI excludes 0.0.

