5.3.4. Secondary Objective 4: functional antibody responses 4 weeks post primary

Secondary objective 4 is to evaluate the functional serum antibody responses (seroresponse rates and GMTs) to the 10 serotypes in PNEUMOSIL, alone and in comparison to the functional antibody responses to these serotypes induced by Prevenar 13 and Synflorix, at 4 weeks post completion of primary vaccination in a subset of 50 subjects per group. For each serotype, the proportion of functional antibody responders (OPA titers ≥ 8) and the GMT at 4 weeks post

primary series will be reported, together with 95% CIs for the proportions and GMTs. Differences in response rates and GMT ratios (PNEUMOSIL versus each comparison group) will also be reported with 95% CIs. Differences between groups will be considered statistically significant if the 95% CI excludes 0.0 (for response rates) or 1.0 (for GMTs).

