8. APPENDIX

8.1.1. Changes to Analysis Plans after Approval of Protocol Version 1.0

- In the event of any randomization errors, supportive analyses based on the Full Immunogenicity Population will be performed according to randomized treatment assignment, rather than treatment received at enrolment. This change was implemented in Version 1.0 of the SAP, prior to any unblinding of any study team members.
- The SAP was updated throughout to reflect the change in the timing of clinic visits in response to the COVID-19 pandemic and related changes to the definition of safety endpoints (Section 2.2.1), procedures for selecting subjects contributing to OPA analysis (Section 3.5), the use of covariates (Section 3.9) in sensitivity and exploratory analyses of immunogenicity data (Sections 5.3.7 and 5.3.8), and the reporting of unsolicited TEAEs with onset after month 9 of age but before V5 (Section 5.4.2). These modifications to the SAP were made blind to individual patient treatment group assignments.
- The SAP was updated (V3) to provide further details regarding non-random selection of subjects for OPA analysis (Section 3.5) and to provide additional details regarding TEAE summaries (5.4.2). These modifications to the SAP were made blind to individual patient treatment group assignments.
- The SAP was updated (V4) to address a change in reports on timing of AE onset in relation to each vaccination (from 14 days to 28 days). Version 4 also clarified that unblinding of non-immunogenicity analyses may occur before immunogenicity results are available due to laboratory delays arising from the COVID-19 pandemic.
- The SAP was updated (V5) to address issues that arose in blind review of data. The decision was made to compare rates of REs between groups using 95% CIs for differences in proportions (rather than p-values) to be consistent with AE summaries. Also specified in the updated SAP is how to report 95% CIs when the response rate is 0% or 100% in both groups being compared, since SAS PROC FREQ does not report a result in this case.

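### SAP 5.1 names no confidence interval method for single-group response proportions; the only written default, Wald, would do badly near 100% if followed, chiefly in the OPA subset

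*SAP*

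**What the plan says.** SAP 5.1 sets out interval methods for four quantities: differences in response proportions (Miettinen-Nurminen score), within-group GMCs and GMTs, between-group ratios, and booster ratios. A single group's response proportion is not among them.

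The results sections nevertheless require that interval. SAP 5.3.2 asks for response rates after the booster "together with 95% CIs for the proportions and for differences between the PNEUMOSIL and comparison groups". SAP 5.3.4 asks for OPA response rates "together with 95% CIs for the proportions and GMTs". SAP 5.3.3, 5.3.5 and 5.3.6 make the same kind of request, and none of the five names a method.

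The only stated default is in the sample-size sections. SAP 3.2 reads "Unless otherwise noted, asymptotic Wald-type CIs will be used when describing proportions, and likelihood Score-type intervals for differences in proportions", and Protocol 12.1 opens the same rule with "Unless otherwise noted, asymptotic Wald-type CIs will be used when describing proportions".

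Version 5 of the SAP added a rule for the boundary, but only for comparisons of two groups. SAP 5.1 says "If the response rate is 100% in each group, then two non-response records (one for each group) will be included", and SAP 8.1.1 describes the change as "how to report 95% CIs when the response rate is 0% or 100% in both groups being compared".

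**The concern.** Response rates for PNEUMOSIL alone, as well as against the comparators, are a stated secondary objective. The study has no hypothesis tests and is sized on precision, so the intervals carry the result.

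The plan can be read in two ways. If the Wald sentence is for planning only, the analysis method is unstated. If it is the default for the analysis, as its wording allows, it is a poor choice near 100%. Rates that high are plausible: the version 5 rule exists because the plan foresees 100% response. Protocol 1.8.2 also reports post-primary OPA response above 92% for all ten serotypes with PNEUMOSIL in VAC-056, and 92-100% in PCV10-002. Within-group intervals in that range would then look more precise than the data allow, or be impossible as printed.

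**Working it through.** **Inputs.** SAP 3.2.3 plans 220 infants per group for IgG and 50 for OPA, with up to 10% lost: 220 × 0.9 = 198 and 50 × 0.9 = 45. SAP 3.5 allows extra specimens "to help ensure at least 45/group contribute to each secondary functional antibody analysis timepoint", so 45 is a target and not a guarantee. The level is two-sided 95%, z = 1.96, z² = 3.84.

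**The plan's own precision figures.** The maximum Wald half-width is z × √(0.25/n). For n = 198 this is 0.0696, and for n = 45 it is 0.1461. They agree with the ceilings of 0.07 and 0.15 in SAP 3.2.3 and Protocol 12.1.

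**The plan's own boundary figure.** SAP 3.2.2 says "If no events of a specific classification occur, then the 95% upper confidence bound for the event rate will be at most 0.017". For 0/220:
- Clopper-Pearson: 1 − 0.025^(1/220) = 0.0166
- Wilson: z²/(n + z²) = 3.84/223.84 = 0.0172
- Wald: 0

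The stated 0.017 therefore did not come from Wald.

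**When a Wald interval breaks.** With k non-responders, the upper limit exceeds 100% when k < z²/(1 + z²/n). That threshold is 3.54 at n = 45, 3.57 at n = 50 and 3.77 at n = 198, so k = 1, 2 or 3 gives an upper limit above 100%. At k = 0 the width is zero.

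**Intervals (%).**

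| Observed | Wald | Wilson | Clopper-Pearson | Wald minus Wilson lower limit (points) |
|---|---|---|---|---|
| 46/50 | 84.5-99.5 | 81.2-96.8 | 80.8-97.8 | 3.3 |
| 49/50 | 94.1-101.9 | 89.5-99.6 | 89.4-99.9 | 4.6 |
| 50/50 | 100-100 | 92.9-100 | 92.9-100 | 7.1 |
| 44/45 | 93.5-102.1 | 88.4-99.6 | 88.2-99.9 | 5.0 |
| 45/45 | 100-100 | 92.1-100 | 92.1-100 | 7.9 |
| 194/198 | 96.0-99.9 | 94.9-99.2 | 94.9-99.4 | 1.1 |
| 197/198 | 98.5-100.5 | 97.2-99.9 | 97.2-100.0 | 1.3 |
| 198/198 | 100-100 | 98.1-100 | 98.2-100 | 1.9 |

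**Coverage (%).** This is the sum of binomial probabilities over all outcomes whose interval contains the true rate.

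| True rate | Wald n=45 | Wilson n=45 | Wald n=50 | Wilson n=50 | Wald n=198 | Wilson n=198 |
|---|---|---|---|---|---|---|
| 80% | 95.1 | 96.2 | 93.8 | 95.1 | 94.8 | 95.0 |
| 90% | 93.6 | 95.9 | 87.9 | 97.0 | 95.0 | 95.7 |
| 92% | 87.6 | 95.2 | 91.2 | 94.1 | 95.1 | 95.2 |
| 95% | 89.9 | 97.6 | 92.0 | 96.2 | 92.3 | 94.9 |
| 98% | 59.7 | 93.9 | 63.5 | 92.2 | 90.1 | 93.5 |
| 99% | 36.4 | 92.5 | 39.5 | 91.1 | 86.2 | 95.0 |

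Wald coverage moves up and down with the true rate. At n = 50 it is 80.7% at a true rate of 94%, between the tabulated 92% and 95%. At n = 198 it falls to 44.8% at a true rate of 99.7%, although the limit is still misplaced by less than 2 points.

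**Chance that an OPA cell shows zero width or an upper limit above 100% (no truncation).**
- n = 50: 0.015 + 0.410 = 43% at a true rate of 92%; 0.077 + 0.683 = 76% at 95%; 0.364 + 0.618 = 98% at 98%.
- n = 45: 0.023 + 0.486 = 51%; 0.099 + 0.714 = 81%; 0.403 + 0.585 = 99%.

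**Ceilings under the alternatives.** The maximum Wilson half-width is (z/2)/√(n + z²): 0.98/√201.84 = 0.0690 and 0.98/√48.84 = 0.1402. Both lie under the stated ceilings. The Clopper-Pearson maxima are 0.0717 and 0.1526, and both exceed them.

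**The case against.** A reader might infer that the plan prescribes Wald for the results and will therefore publish invalid intervals. The documents do not support that. The sentence sits among sample-size assumptions and yields to anything noted elsewhere. The zero-event bound in the same section is not Wald. Earlier trials in the programme did not use it near 100% either: VAC-017 states Clopper-Pearson, and the VAC-056 row for Synflorix type 1 (717/724) is printed as 98.0-99.6, which is the Clopper-Pearson interval, whereas the Wald lower limit is 98.3. An unstated method is at least as likely as a bad one. The table shells, kept in a separate document, may name it. Precedent and shells do not replace a rule in the SAP, so the gap stands.

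The evidence for high rates is also partial. The VAC-056 figure is for PNEUMOSIL after three doses, and PCV10-002 tested OPA in 25 toddlers per group. Against it, Prevenar 13 type 1 OPA response was 84.6% in VAC-017 infants. The Synflorix 6A OPA GMT in VAC-056 was 7.06, below the threshold of 8. The pre-booster visit is an analysis time point too, and the figures above do not address it. Many cells may lie well below 95%. This narrows where the problem bites but does not remove it.

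Limits above 100% could be truncated at printing; the documents are silent on this. Truncation would not repair the lower limits or the zero width.

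Finally, no decision rule uses these intervals. That is correct, and it keeps the point small.

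**Conclusion.** The point holds as a minor one. A required analysis has no stated interval method, and the one default in writing is unsuitable near 100%.

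If Wald is followed, OPA coverage is about 88-92% at true rates of 92% and 95% and 60-64% at 98%. Lower limits are then roughly 3 to 8 points too high for observed rates of 92-100%. For IgG the displacement is 1-2 points, at about 98% and above. At true rates of 80% and 90%, OPA coverage is about 88-95%.

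These sizes depend on Wald being used, on 45 to 50 OPA and 198 IgG results per group, and on true rates that are unknown for this 2+1 infant schedule. The primary GMC analysis and the Miettinen-Nurminen differences are untouched, so the material gives no ground for doubting the trial's main comparisons.

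**What to change.** Add one sentence to SAP 5.1: 95% intervals for all single-group response proportions, including 0% and 100%, are Wilson score intervals. The stated half-width ceilings then remain true. Alternatively, name Clopper-Pearson for consistency with VAC-017, and restate the ceilings in SAP 3.2.3 as about 0.072 (n = 198) and 0.153 (n = 45).

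In SAP 3.2, limit the Wald sentence to planning, and log the change in SAP 8.1.1. Protocol section 12 lets the SAP document changes of analysis method but ties this to approval before interim unblinding of the CRO's statistical staff. The documents do not date that unblinding. The log should therefore give the timing of the change relative to it, and should not assert that no protocol amendment is needed.

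The cost is a sentence, a clause and a software option, plus wider intervals near 100%. From Wald to Wilson, width goes from 7.8 to 10.1 points at 49/50, from 8.6 to 11.2 at 44/45, and from 2.0 to 2.7 at 197/198. Wilson is not perfect at the extreme: its coverage is 92-94% at a true rate of 98% with n = 45 to 50, and 86-87% at 99.7%. Clopper-Pearson stays at or above 95% at the rates checked, at the price of being conservative.
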